#### 5.2.4 Subgroup analyses

Planned exploratory subgroup analyses will be performed for the primary outcome measure only and will include:

- Baseline HbA1c: 7.5%-9.0%; >9.0%-11%
- Treatment modality: MDI; CSII
- Prior participation in structured education course: yes; no
- Age group at recruitment (Visit 1): 16 <30; 30 to <45; 45 to <60; >=60 years
- Education: < Bachelor's degree; >= Bachelor's degree
- Hypoglycaemia Unawareness: Yes (Clarke score >3); No (Clarke score ≤3)
- Deprivation Index Quintile: (as a categorical variable, although exploratory analysis will include consideration of a linear trend or combination of adjacent categories)
- Sex: Male; Female

- Ethnic group: Categorisation will be determined by the number in individual ethnic groups. It is expected that this will take the form of white vs. non-white due to the low expected numbers in separate non-white categories, but further exploratory analyses may be performed (e.g. white vs. South Asian vs. 'other')
- PHQ-9: Mild or none depression (items sum score <10); Moderate or severe depression (items sum score  $\geq 10$ ).

### 5.3 Missing data

Should we have more than 10% missing HbA1c at 24 weeks (or more than a 10% difference between missing data percentages in the two arms), multiple imputation will be used in order to implement a more complete ITT analysis of the substantive ANCOVA model. The imputation model will include baseline and 12-week HbA1c, all the baseline variables used in the outcome model and any other recorded variables found to be predictive of missing the 24-week outcome in exploratory analyses (via a logistic regression model, with terms included using a 10% significance level). A minimum of 50 imputations will be performed, although this will be increased if the percentage of missing data is greater than expected. We will perform multiple imputation by chained equations (MICE).

Complete cases analyses will be implemented for all secondary outcomes. Should we have up to 30% missing items for any subscale (or overall questionnaire if no subscales), the missing item will be imputed by the mean response of the rest items completed within participant for that particular subscale. If more than 30% missing items the response to this subscale will be set to missing, as will be the overall response of the questionnaire.

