26.2 Appendix 2: Glucose Monitoring Satisfaction Survey

The Glucose Monitoring Satisfaction Survey (GMSS)

Version: Type 1 Diabetes

We are interested in your thoughts and feelings regarding your current glucose monitor.

For each item below, circle the number that best indicates how much you agree or disagree with each statement as it pertains to your current monitor. Some patients use more than one monitor. Please consider the monitor you use the most or consider to be your primary monitor when answering these questions.

	My current monitor:	Strongly disagree	Disagree	Neutral	Agree	Strongly agree
1	Helps me feel more satisfied with how things are going with my diabetes.	1	2	3	4	5
2	Makes me think about diabetes more than I want to.	1	2	3	4	5
3	Takes too much time to use.	1	2	3	4	5
4	Doesn't seem to be as accurate as I would like it to be.	1	2	3	4	5
5	Makes me worry a lot.	1	2	3	4	5
6	Is too much of a hassle to use.	1	2	3	4	5
7	Gives me numbers that I don't entirely trust.	1	2	3	4	5
8	Helps me feel less restricted by diabetes.	1	2	3	4	5
9	Makes me feel more frustrated with my diabetes.	1	2	3	4	5

10	Helps me be more spontaneous in my life.	1	2	3	4	5
11	Causes too many skin irritations or bruises.	1	2	3	4	5
12	Often gives me results that don't make sense.	1	2	3	4	5
13	Makes me feel more down and depressed.	1	2	3	4	5
14	Helps me be more open to new experiences in life.	1	2	3	4	5
15	Is too painful to use.	1	2	3	4	5

Scoring instructions:

The GMS for Type 1 Diabetes contains four subscales as well as a total score. Each can be obtained by calculating the mean item response score for the groups of items below.

Openness (higher scores indicate greater openness): Items 1, 8, 10, 14

Emotional Burden (higher scores indicate greater burden): Items 2, 5, 9, 13

Behavioral Burden (higher scores indicate greater burden): Items 3, 6, 11, 15

Trust (higher scores indicate greater trust): Reverse code items 4, 7, 12

Total scale (higher scores indicate greater satisfaction): Mean of items 1-15 (reverse code items: 2-7, 9, 11-13, and 15)

26.3 Appendix 3: Patient Health Questionnaire 9

Fill in the boxes with pen or pencil to mark your answers.

A. Over the last 2 weeks, how often have you been bothered by any of the following problems?

	Not at all 0	Several days 1	More than half the days 2	Nearly every day 3
1. Little interest or pleasure in doing things				

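### Under the SAP's 30% missing-item rule, one skipped item always voids the three-item GMSS Trust subscale and, with it, the 15-item GMSS total

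*SAP*

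**What the plan says.** SAP section 5.3 sets one missing-item rule for all questionnaires. The tolerance is worded "Should we have up to 30% missing items for any subscale (or overall questionnaire if no subscales"). Within it, "the missing item will be imputed by the mean response of the rest items completed within participant for that particular subscale". Above it, the subscale "will be set to missing, as will be the overall response of the questionnaire". The same section adds: "Complete cases analyses will be implemented for all secondary outcomes".

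Protocol Appendix 2 says that the GMSS "contains four subscales as well as a total score". Openness, Emotional Burden and Behavioral Burden have four items each. The fourth subscale is "Trust (higher scores indicate greater trust): Reverse code items 4, 7, 12", which is three items. The total is "Mean of items 1-15 (reverse code items: 2-7, 9, 11-13, and 15"). Appendix 2 gives no rule for missing items.

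SAP section 5.4 compares the GMSS total and each subscale between arms by ANCOVA, adjusted for the baseline value of the same score.

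**The concern.** A percentage limit behaves differently on short and long scales. With three items, the smallest possible non-zero missing fraction already exceeds 30%, so the imputation provision can never operate for Trust. Because a void subscale also voids the questionnaire, that zero tolerance passes to the total. The whole-questionnaire 30% test does not rescue it, since that test is reserved for instruments without subscales.

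The resulting order is perverse: a form with one blank can lose its total while a form with three blanks keeps it. Each void score costs a participant in an ANCOVA that needs both the baseline and the follow-up value, and no multiple imputation is planned for these scores. Skipped items are plausible, because the questionnaires are on paper (Protocol section 15) and are posted where necessary (Protocol section 9.2.2).

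**Working it through.** The documents derive no figure from this rule, so there is none to reproduce.

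**Step 1: tolerance by scale** (item counts from Protocol Appendix 2, limit from SAP 5.3)

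- Trust: 1/3 = 33.3% > 30%, so no skip is tolerated.
- Openness, Emotional Burden, Behavioral Burden: 1/4 = 25% ≤ 30% and 2/4 = 50% > 30%, so one skip each is tolerated.
- For comparison, the nine-item PHQ-9 tolerates two skips (2/9 = 22.2%).

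**Step 2: two forms side by side**

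- One Trust item blank: 1/15 = 6.7% missing. Trust void, total void.
- One item blank in each four-item subscale: 3/15 = 20% missing. All four subscales scored, total kept.

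This step needs no assumption.

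**Step 3: size of the loss**

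Assume each item is skipped with probability p, independently across items and visits. The documents give no value for p; 0.5% to 5% is shown as a range.

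- P(Trust scorable) = T = (1−p)³
- P(a four-item subscale scorable) = S = (1−p)⁴ + 4p(1−p)³
- P(total void at one visit) = 1 − T·S³
- P(total void at baseline or follow-up) = 1 − (T·S³)²

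For p = 1%: T = 0.9703, S = 0.99941, S³ = 0.99822, T·S³ = 0.9686. The total is void in 3.1% at one visit and in 1 − 0.9686² = 6.2% at either.

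For p = 2%: T = 0.9412, S = 0.99766, S³ = 0.99301, T·S³ = 0.9346. The total is void in 6.5% at one visit and in 12.7% at either.

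**Step 4: the same with Trust scored from at least two of three items**

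Replace T by T′ = (1−p)³ + 3p(1−p)².

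- p = 1%: T′ = 0.99970, T′·S³ = 0.99793, so 0.2% void at one visit and 0.4% at either.
- p = 2%: T′ = 0.99882, T′·S³ = 0.99183, so 0.8% and 1.6%.

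| Assumed p | Trust void now, one visit | Total void now, one visit | Total void now, either visit | Total void after change, one visit |
|---|---|---|---|---|
| 0.5% | 1.5% | 1.5% | 3.0% | 0.05% |
| 1% | 3.0% | 3.1% | 6.2% | 0.2% |
| 2% | 5.9% | 6.5% | 12.7% | 0.8% |
| 5% | 14.3% | 17.8% | 32.5% | 4.8% |

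Most of the present loss of the total comes from Trust. As a rough scale only, 6.2% and 12.7% of 128 participants (the evaluable number planned for HbA1c, Protocol section 14.1) are about 8 and 16 people.

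**The case against.** The rule can be defended. It reports a total spanning four domains only when each domain can be scored, which is coherent. Appendix 2 does not say whether the developers accept Trust from two items, so calling the loss needless is a judgement. It is better supported for the total, where 14 of 15 answers are in hand, than for Trust itself. These points stand, and they shape the fix.

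The size is also open to challenge. If skips cluster, for instance as whole pages left blank, fewer scores are lost to a single stray Trust item and more are lost under any rule. The protocol plans data queries (section 16) but does not say that they recover skipped answers. Protocol section 14.4 treats GMSS as descriptive, and the SAP places it with the process evaluation.

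Four stronger readings are tempting, and the documents do not support them:

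- *Survival of a score depends only on which item is skipped.* It depends on completeness too: two blanks in any four-item subscale also void the total.
- *The total should be judged by 30% of its 15 items alone.* Up to 4/15 = 26.7% could then be blank, so a total would be reported with all of Trust (3/15 = 20%) or a whole four-item subscale unanswered. The present clause prevents that.
- *All subscales should tolerate one third missing.* If the two D-FISQ sections (six and nine items, Protocol Appendix 5) count as subscales, their tolerance would rise from one to two items and from two to three. That would loosen a secondary outcome to mend a three-item subscale.
- *The loss biases the comparison of arms.* The Trust items ask about the accuracy of the monitor, and the arms use different monitors, so unequal loss is possible. The documents hold no data on it.

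**Conclusion.** The point holds as a narrow one. That one skipped Trust item voids both Trust and the GMSS total follows directly from SAP 5.3 and Protocol Appendix 2, and no section exempts short subscales. The amount lost is illustrative: the 6.2% and 12.7% figures rest on assumed skip rates of 1% and 2% and on independence across items and visits. Severity is minor. The other three GMSS subscales are still scored when Trust is void, and no primary, safety or powered comparison is touched.

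**What to change.** After checking the instrument's scoring guidance, add one sentence to SAP 5.3: GMSS Trust is scored when at least two of its three items are answered, with the missing item set, after reverse-coding, to the mean of the other two. A single skipped Trust item then voids neither Trust nor the total.

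Keep the requirement that every subscale be scorable before a total is reported, and leave the 30% rule as it stands for the other questionnaires.

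The cost is one sentence, with no change to data collection. The downside is that a Trust score resting on two items is slightly noisier.

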### 5.4 Additional analyses

The process evaluation (utility and acceptability) will include:

- Summary statistics (mean, standard deviation, range) of (i) the average number of scans per day (7:00-23:00), (ii) per night (23:00-7:00), (iii) over the full 24-hour period, and (iv) the average number of days of usage per week for the FLS2 trial arm
- Summary statistics (mean, standard deviation, and range, where appropriate) and ANCOVA will be used to explore and compare each of:
  - the average number of finger-stick glucose level tests per calendar day;
  - patient satisfaction with treatment (DTSQ total score);

- patient satisfaction with monitoring (GMSS total score; Openness subscale score; Emotional Burden subscale score; Behavioral Burden subscale score ; Trust subscale score).

by trial arm, adjusting for the baseline value of the respective outcome and the other baseline variables included in the minimisation allocation algorithm as covariates.

Additional analysis will include summary statistics (number and frequency) of initialisation of concomitant diabetes medications during the follow up period.

The analysis of the primarily *qualitative* 'Expectations and experience' questionnaire is not covered in this document. The quantitative results will be integrated into the broader process evaluation which is described more fully in the trial protocol.

## 5.5 Harms

All relevant adverse events (AEs) related to:

1. Frequency of severe hypoglycaemic episodes as defined by American Diabetes Association
2. Frequency of significant ketosis events (plasma ketones  $>3\text{mmol/l}$ )
3. Nature and severity of other adverse events including the following categories:
  - a. Hospital admissions
  - b. Skin reactions

will be reported. The number of events and the number of participants with at least 1 event across treatment arms will be reported. We will also report all individual SAEs/AEs by treatment arms. Summary measures will be frequencies and percentages (%) across treatment arms.

## 5.6 Statistical software

Analyses will be undertaken in Stata version 14.0^9 or later.

